10.10.2. Introduction

10.10.2.1. Substudy Rationale

Substudy B is a Phase 1/2 randomized, single-blind (sponsor-unblinded) substudy to evaluate the safety and immunogenicity of the following vaccination schedules:

In participants 65 to 85 years of age:

- 2 Doses of qIRV encoding 2 A strains and 2 B strains at a dose level of CCl administered 21 days apart.
- 2 Doses of licensed QIV, administered 21 days apart (as a control group).
- A dose of licensed QIV followed by a dose of bIRV encoding 2 A strains at a dose level of either CCl., administered 21 days apart.
- A dose of licensed QIV administered concurrently in the opposite arm with bIRV encoding 2 A strains at a dose level of either CC.
- A dose of bIRV encoding 2 A strains at a dose level of CC administered concurrently in the opposite arm with bIRV encoding 2 B strains at a dose level of CC.
- A dose of qIRV encoding 2 A strains and 2 B strains at the following dose level combinations:
 - CCI
- A dose of licensed QIV (as a control group).

In participants 18 to 64 years of age:

- A dose of qIRV encoding 2 A strains and 2 B strains at a dose level of CC
- A dose of qIRV encoding 2 A strains and 2 B strains at a dose level of CCI

10.10.2.2. Background

See Section 2.2.

10.10.2.3. Benefit/Risk Assessment

Benefits to individual participants enrolled in Substudy B may be:

• Contributing to research to help others.

Please see Section 2.3.3 for details of the SRSDs relating to the study intervention used in Substudy B.

10.10.3. Objectives, Endpoints, and Estimands (Substudy B)

For the purposes of the study estimands:

• Seroconversion is defined as an HAI titer <1:10 prior to vaccination and ≥1:40 at the time point of interest, or an HAI titer of ≥1:10 prior to vaccination with a 4-fold rise at the time point of interest.

Objectives	Estimands	Endpoints
Primary Safety:	Primary Safety:	Primary Safety:
To describe the safety and tolerability of modRNA influenza vaccines when administered in differing vaccination schedules in adults 18 to 64 and 65 to 85 years of age	In participants receiving at least 1 dose of study intervention, the percentage of participants reporting: • Local reactions for up to 7 days following each vaccination • Systemic events for up to 7 days following each vaccination • AEs from the first vaccination to 4 weeks after the last vaccination • SAEs from the first vaccination to 6 months after the last vaccination	 Local reactions (pain at the injection site, redness, and swelling) Systemic events (fever, fatigue, headache, chills, vomiting, diarrhea, new or worsened muscle pain, and new or worsened joint pain) AEs SAEs
	The percentage of participants with: • Abnormal troponin I laboratory values 2 days after the last vaccination	Troponin I laboratory parameters detailed in Section 10.2
	The percentage of participants with: New ECG abnormalities 2 days after the last vaccination	ECG abnormalities consistent with probable or possible myocarditis or pericarditis as defined in Section 8.2.7
Secondary:	Secondary:	Secondary:
To describe the immune responses elicited by modRNA influenza vaccines when administered in differing vaccination schedules in adults 65 to 85 years of age	 In participants complying with the key protocol criteria (evaluable participants) at Day 21 (if applicable) and 1, 4, and 8 weeks after receipt of the last vaccination: HAI GMTs before Vaccination 1, prior to Vaccination 2 (Day 21, if applicable), and at 1, 4, and 8 weeks after receipt of the last vaccination HAI GMFR from before Vaccination 1 to prior to Vaccination 2 (Day 21, if applicable) and to 1, 4, and 8 weeks after receipt of the last vaccination The proportion of participants achieving HAI seroconversion for each strain prior to Vaccination 2 (Day 21, if applicable) and at 1, 4, and 8 weeks after receipt of the last vaccination 	HAI titers for each strain targeted by the study vaccine

PFIZER CONFIDENTIAL

Objectives	Estimands	Endpoints
	• The proportion of participants with HAI titers ≥1:40 for each strain before Vaccinations 1 and 2 (Day 21, if applicable) and at 1, 4, and 8 weeks after receipt of the last vaccination	
	In participants having received at least 1 dose of a quadrivalent vaccine, complying with the key protocol criteria (evaluable participants), at Day 21 (if applicable) and at 1, 4, and 8 weeks after receipt of the last vaccination: • The proportion of participants achieving HAI seroconversion for all strains prior to Vaccination 2 (Day 21, if applicable) and at 1, 4, and 8 weeks after receipt of the last vaccination • The proportion of participants with HAI titers ≥1:40 for all strains before Vaccinations 1 and 2 (Day 21, if applicable) and 1, 4, and 8 weeks after receipt of the last vaccination	HAI titers for each strain targeted by the study vaccine
To describe the immune responses elicited by qIRV in adults 18 to 64 years of age	 In participants complying with the key protocol criteria (evaluable participants) at 1, 4, and 8 weeks after receipt of vaccination: HAI GMTs before vaccination and at 1, 4, and 8 weeks after receipt of vaccination HAI GMFR from before vaccination to 1, 4, and 8 weeks after receipt of vaccination The proportion of participants achieving HAI seroconversion for each strain at 1, 4, and 8 weeks after receipt of vaccination The proportion of participants with HAI titers ≥1:40 for each strain before vaccination and at 1, 4, and 8 weeks after receipt of vaccination The proportion of participants achieving HAI seroconversion for all strains at 1, 4, and 8 weeks after receipt of vaccination The proportion of participants with HAI titers ≥1:40 for all strains before vaccination and 1, 4, and 8 weeks after receipt of vaccination 	HAI titers for each strain targeted by the study vaccine

Objectives	Estimands	Endpoints
Tertiary/Exploratory:	Tertiary/Exploratory:	Tertiary/Exploratory:
CCI		

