6. STUDY INTERVENTION(S) AND CONCOMITANT THERAPY

Study intervention is defined as any investigational intervention(s), marketed product(s), placebo, medical device(s), or study procedure(s) intended to be administered to a study participant according to the study protocol.

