- Enrollment will be controlled for the first group in which the total dose of modRNA vaccine administered at a single vaccination is **CCI**, and also for the first group in which the total dose is **CCI** as follows:
 - No more than 5 participants can be vaccinated on the first day.
 - Vaccination of the remaining participants will commence no sooner than 24 hours after the fifth participant received his or her vaccination.
- Safety and immunogenicity data accumulated at least 1 week following the last vaccination in each group will be reviewed by the sponsor's IRC and, if deemed acceptable, an additional 120 participants 65 to 85 years of age will be enrolled in that group (expanded enrollment).
- If a group is not selected for enrollment expansion or, based on review of immunogenicity data at the 4-week time point, at the sponsor's discretion, subsequent collection of blood samples from participants in that group may be halted and/or not analyzed.

As detailed above, Substudy B expanded enrollment will comprise group(s) of 120 participants following the vaccination schedule(s) as selected by the sponsor's IRC from initial enrollment. Additionally,

• 240 participants 18 to 64 years of age will be randomized 1:1 to receive either a single dose of CCI qIRV (encoding 2 A strains and 2 B strains at a dose level of CCI qIRV (encoding 2 A strains and 2 B strains at a dose level of CCI.).

- Expanded-enrollment groups may also be included that comprise only the first dose from 2-visit—schedule initial enrollment groups, eg, 1 dose of qIRV at a dose level of ...
- At the discretion of the sponsor's IRC, a control group of 120 participants may be enrolled during expanded enrollment who will receive a dose of licensed QIV followed by placebo, administered 21 days apart.

Therefore, Substudy B expanded enrollment will consist of approximately 120 to 1725 participants, depending on the number of groups selected to progress to expanded enrollment.

Stopping rules will apply throughout initial and expanded enrollment as detailed in Section 10.10.8.6.

All participants will be asked to complete a reactogenicity e-diary for 7 days following each vaccination. Blood samples of approximately 50 mL will be collected for immunogenicity assessments prior to Vaccination 1, prior to Vaccination 2 (if applicable), and at 1, 4, and 8 weeks after the participant's last vaccination.

The total duration of the study for each participant will be up to approximately 8 months.

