2.2.1. Primary Safety Estimands

The primary estimands for the primary objective will follow the treatment policy strategy from the EMA ICH E9 (R1) addendum¹ and estimate the safety percentages regardless of the occurrence of intercurrent event(s) or rescue medication use. The analyses will be based on the actual vaccine received.

In participants receiving at least 1 dose of study intervention:

• The percentage of participants reporting prompted local reactions up to 7 days following each vaccination.

This estimand includes the following attributes:

- Treatment: 1-Visit schedules or 2-visit schedules with modRNA, licensed QIV, and/or placebo or their combinations as listed in Table 2.
- Population: Safety population for 1-visit schedules and Vaccination 1 safety population or Vaccination 2 safety population for 2-visit schedules as defined in Section 4.
- Variable: Presence/absence of prespecified local reactions up to 7 days after each vaccination.
- Intercurrent event(s): For participants who discontinue receipt of study intervention or discontinue participation in the study.
- Population-level summary: Percentage and associated 2-sided 95% CI of participants reporting local reactions in each vaccine group.
- The percentage of participants reporting prompted systemic events up to 7 days following each vaccination.

- Treatment: 1-Visit schedules or 2-visit schedules with modRNA, licensed QIV, and/or placebo or their combinations as listed in Table 2.
- Population: Safety population for 1-visit schedules and Vaccination 1 safety population or Vaccination 2 safety population for 2-visit schedules as defined in Section 4.
- Variable: Presence/absence of prespecified systemic events up to 7 days after each vaccination.
- Intercurrent event(s): Participants discontinue.

- Population-level summary: Percentage and associated 2-sided 95% CI of participants reporting systemic events in each vaccine group.
- The percentage of participants reporting AEs from the first vaccination to 4 weeks after the last vaccination.

This estimand includes the following attributes:

- Treatment: 1-Visit schedules or 2-visit schedules with modRNA, licensed QIV, and/or placebo or their combinations as listed in Table 2.
- Population: Safety population as defined in Section 4.
- Variable: Presence of AEs from the first vaccination to 4 weeks after the last vaccination.
- Intercurrent event(s): Participants discontinue.

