2.3. Study Design

2.3.1. Overall Design

This is a Phase 1/2 randomized, single-blinded (sponsor-unblinded) study to evaluate the safety, tolerability, and immunogenicity of a modRNA vaccine against influenza in healthy individuals from 18 through 85 years of age.

In participants from 65 through 85 years of age:

Participants will be randomized to and will be blinded to which 1-visit or 2-visit vaccination schedules they will receive:

2-Visit Schedules

- 2 Doses of qIRV encoding 2 A strains and 2 B strains at a dose level of CCl
 administered 21 days apart
- 2 Doses of licensed QIV, administered 21 days apart (as a control group)
- A dose of licensed QIV following by a dose of bIRV encoding 2 A strains at a dose level of either CCl administered 21 days apart

1-Visit Schedules

- A dose of licensed QIV administered concurrently in the opposite arm with bIRV encoding 2 A strains at a dose level of either CC
- A dose of bIRV encoding 2 A strains at a dose level of CCl administered concurrently in the opposite arm with bIRV-encoding 2 B strains at a dose level of CCl
- A dose of qIRV encoding 2 A strains and 2 B strains at the following dose level combinations:

• A dose of licensed QIV (as a control group)

Substudy B enrollment will be separated into an initial and expanded enrollment. Depending on the availability of study intervention and operational prioritization, groups in Substudy B may not all be randomized concurrently; however, a minimum of 2 groups will be open for randomization at any 1 time.

During initial enrollment, each group (vaccine formulation/dose level, or control) will comprise 15 participants. Hence, Substudy B initial enrollment will comprise approximately 165 participants.

Substudy B expanded enrollment will comprise group(s) of 120 participants following the vaccination schedule(s) as selected by the sponsor's IRC from initial enrollment. If deemed acceptable, an additional 120 participants will be enrolled in that group (expanded enrollment). Additionally,

- Expanded-enrollment groups may also be included that comprise only the first dose from 2-visit—schedule initial-enrollment groups, eg, 1 dose of qIRV at a dose level of CCI.
- A control group of 120 participants will be enrolled during expanded enrollment who will receive a dose of licensed QIV followed by placebo, administered 21 days apart.

In participants from 18 through 64 years of age:

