b. At the discretion of the sponsor's IRC, a control group of 120 participants may be enrolled during the expanded enrollment who will receive a dose of licensed QIV followed by placebo, administered 21 days apart.

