5.2.1.1. Safety Data

All safety analyses will be performed on the safety populations.

For safety data, as defined in Section 3.1.1, the exact 2-sided 95% CIs using the Clopper and Pearson method will be provided by vaccine group for all primary safety endpoints and for proportions of participants reporting local reactions, systemic events, AEs (including immediate AEs), SAEs, abnormal troponin I values, and new ECG abnormalities. The 95% CI for the between-group difference for binary endpoints will be calculated using the Miettinen and Nurminen method.

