6.1.1.3. Adverse Events

6.1.1.3.1. Main Analysis

- Estimand: The percentage of participants reporting AEs from the first vaccination through 4 weeks after the last vaccination.
- Estimand strategy: Treatment policy (Section 2.2.1).
- Analysis set: Safety population (Section 4).
- Analysis time point: Day 1 from the first vaccination through 4 weeks after the last vaccination.
- Analysis methodology: Descriptive summary statistics.
- Intercurrent events and missing data: For participants who discontinue, all collected data will be included; missing AE dates will be imputed as described in Pfizer's Vaccine Statistics Rulebook.
- Reporting results: The number of participants with AEs from the first vaccination though 4 weeks after the last vaccination (n), proportion, and associated 2-sided Clopper-Pearson 95% CI will be presented for any AE, immediate AEs, severe AEs, related AEs, and AEs leading to withdrawal for each SOC, and each PT within each SOC, by vaccine group.

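### Substudy B: the AE window is about 28 days in a 1-visit group but about 49 days in the optional QIV/placebo control, and the SAP provides for between-group AE intervals without a common window (minor)

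*Protocol*

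**What the plan says.** **Window.** Protocol 10.10.3 defines the AE estimand as "AEs from the first vaccination to 4 weeks after the last vaccination". SAP 6.1.1.3.1 repeats it: "The percentage of participants reporting AEs from the first vaccination through 4 weeks after the last vaccination". Neither gives a second window, a per-vaccination AE summary or an exposure adjustment. The Vaccination 1 safety population in SAP 4 is used for reactogenicity, troponin and ECG, not for AEs.

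**Placebo counts.** Protocol 6 includes placebo in its definition of study intervention. Protocol Table 6 makes it Vaccination 2 for Group 12. The treatment attribute in SAP 2.2.1 covers "1-Visit schedules or 2-visit schedules with modRNA, licensed QIV, and/or placebo or their combinations as listed in Table 2".

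**Which groups could meet.** Protocol 10.10.4.1 leaves the QIV/placebo group of 120 to the internal review committee. In SAP 2.3.1 the text reads "A control group of 120 participants will be enrolled during expanded enrollment who will receive a dose of licensed QIV followed by placebo", while footnote b of its Table 2 reads "a control group of 120 participants may be enrolled during the expanded enrollment who will receive a dose of licensed QIV followed by placebo". Single-dose groups are also possible at that stage: "Expanded-enrollment groups may also be included that comprise only the first dose" (Protocol 10.10.4.1). SAP 5.2 analyses initial and expanded enrollment separately.

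**Intervals.** SAP 6.1.1.3.1 and Protocol 10.10.9.3.2 report AEs within group, with Clopper-Pearson intervals. SAP 5.2.1.1, on safety data, lists AEs among the proportions to be reported and then adds: "The 95% CI for the between-group difference for binary endpoints will be calculated using the Miettinen and Nurminen method". It names no pair of groups and no window.

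**The concern.** A cumulative AE percentage grows with the length of follow-up. When the end of follow-up is tied to the last injection and one group's last injection is a saline dose three weeks after the vaccine, that group accumulates about three more weeks of ordinary background AEs. Two identical vaccines would then show different AE percentages. The direction is fixed: the QIV/placebo control looks worse and a 1-visit modRNA group looks better tolerated.

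The exposed comparison is a 1-visit group aged 65 to 85 against QIV/placebo at the expanded stage. A 2-visit group against QIV/placebo has matching windows. So do two 1-visit groups, such as Groups 13 and 14. Reactogenicity is not affected, because it is counted for 7 days after each vaccination.

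**Working it through.** **The plan's own figures.** The only AE calculation in the documents is Protocol Table 4. At N = 120 and a true rate of 1%, 1 − 0.99^120 = 0.7006, which matches the stated 0.70. The Substudy B total also reproduces: 165 + 13 × 120 = 1725. Neither bears on window length.

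**Windows.** Visit 203 is 19 to 23 days after Visit 201 (Protocol 10.10.8.8.4). Visit 206 is 26 to 30 days after the last vaccination (10.10.8.8.7).
- 1-visit group: 26 to 30 days, nominally 28.
- QIV/placebo: 19 + 26 = 45 to 23 + 30 = 53 days, nominally 21 + 28 = 49.
- Nominal ratio: 49/28 = 1.75.

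**Model (assumed).** Let p28 be the 28-day AE risk, the same for both vaccines. Let f be the share of the 28-day cumulative hazard that is constant background. The rest is a burst after the first dose that placebo does not repeat. Over 49 days the cumulative hazard is multiplied by (1 − f) + f × 49/28 = 1 + 0.75f, so

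p49 = 1 − (1 − p28)^(1 + 0.75f).

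**Chance that the interval excludes 0.** With 120 per group, sum the joint binomial probabilities over all outcomes where the Miettinen-Nurminen score at zero difference, (pC − p1)/√[p̄(1 − p̄)(2/120)(240/239)], exceeds 1.96. Here pC and p1 are the observed control and 1-visit proportions and p̄ is the pooled one.

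| f | p28 | p49 | Control excess (points) | P(95% CI excludes 0, favouring 1-visit) |
|---|---|---|---|---|
| 1 (constant hazard) | 10% | 16.8% | +6.8 | 34.3% |
| 1 | 20% | 32.3% | +12.3 | 58.9% |
| 1 | 30% | 46.4% | +16.4 | 75.45% |
| 0.5 | 10% | 13.5% | +3.5 | 12.9% |
| 0.5 | 20% | 26.4% | +6.4 | 21.8% |
| 0.5 | 30% | 38.8% | +8.8 | 29.8% |
| 0.25 | 10% | 11.8% | +1.8 | 6.3% |
| 0.25 | 20% | 23.3% | +3.3 | 9.0% |
| 0.25 | 30% | 34.5% | +4.5 | 11.2% |

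With equal windows the same one-directional probability is 2.5%, 2.6% and 2.5% at the three risks.

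**Scale.** The 95% half-width for a difference at 120 per group, 1.96√[2p(1 − p)/120], is 7.6, 10.1 and 11.6 points at 10%, 20% and 30%. The excess is larger than this only with constant hazard at 20% and 30%.

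**Visit-window extremes**, with the burst inside the first 26 days. At 30 against 45 days, f = 0.25 and 10% risk: 10.17% against 11.43%, or +1.3 points. At 26 against 53 days, f = 1 and 30% risk: 28.19% against 49.09%, or +20.9 points.

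**The case against.** The strongest reply is that the plan commits to no such comparison. The objective is descriptive and there are no hypotheses. The synopsis, Protocol 10.10.9.3.2, SAP 2.2.1 and SAP 6.1.1.3.1 all report AEs within group. The sentence in SAP 5.2.1.1 repeats the general one in SAP 5.2.1 and closely follows Protocol 9.3.1.1, so it can be read as naming a method in case a difference is computed. Where the protocol wants a difference it specifies groups, endpoint and time point, as for Substudy A seroconversion in 10.9.9.3.3. This stands. A reader might infer that the primary safety contrast is biased as planned, but the documents name no AE contrast that could be so described.

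Several conditions must also hold together. The QIV/placebo group and a 1-visit group aged 65 to 85 must both be expanded, and the two must be compared. Group 8, single-dose QIV, could be expanded as a window-matched control. This also stands, although nothing requires that expansion and QIV/placebo is the only control named for the expanded stage.

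The magnitudes rest on assumed rates and time courses, and 75% is the corner of the grid. In both burst scenarios the excess is smaller than the half-width of the interval. How often an interval excludes 0 is a testing measure in a study that tests nothing. These limits are accepted, but a shifted estimate and interval mislead without any test.

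Finally, nothing is lost for good, because onset dates are collected and the table can be re-cut at reporting. That makes the point minor. It does not remove the case for fixing the window in advance.

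**Conclusion.** The unequal windows follow directly from the protocol: about 28 days against about 49. As within-schedule descriptions the AE percentages need no correction. The gap is narrow: SAP 5.2.1.1 provides for between-group intervals on a list that includes AEs and sets no common window. If that is applied to a 1-visit expanded group against QIV/placebo, the result is biased in favour of the 1-visit group.

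The size cannot be fixed from the documents. It runs from about +2 to +16 points for assumed 28-day risks of 10% to 30%, nominal visit days, no vaccine difference and a background share between one quarter and all of the 28-day hazard. This is a minor, inexpensive improvement to the SAP, not a defect in a planned primary comparison.

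**What to change.** Keep the full-course AE percentage as the description within each schedule. Add to SAP 5.2.1.1 and 6.1.1.3:

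*Any AE difference between a 1-visit group and the QIV/placebo group will count AEs with onset from Vaccination 1 through 28 days after Vaccination 1 (vaccination day = day 0) in both groups.*

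The day-0 convention has to be written out, because the e-diary sections count the vaccination day as Day 1.

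The data already exist. The earliest in-window Visit 206 in a 1-visit group is at 26 days, and Protocol 8.3.1 requires AEs up to 48 hours after that blood draw to be recorded: 26 + 2 = 28 days. This holds where the draw is taken; Protocol 10.10.8.8.7 lets the sponsor waive it by group.

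The cost is one sentence and one extra table, with no new visit or sample. Two imperfections remain:
- Between 28 − 23 = 5 and 28 − 19 = 9 days of post-placebo AEs stay in the control. If placebo added 10% of the 28-day hazard, the residual would be 1 − (1 − p28)^1.1 − p28, or +0.9, +1.8 and +2.5 points at 10%, 20% and 30%.
- Contact timing still differs. Visit 202 is held only in initial enrollment, so the expanded control's first scheduled visit after Vaccination 1 is at 19 to 23 days, against 2 to 4 days in a 1-visit group. The effect of this on AE reporting is not quantified here.
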